Lesion-related mortality	Defined as all deaths during hospitalization for index endovascular procedure and within 30 days of the index endovascular procedure or any secondary procedures due to the treated pathology, or the effectiveness of the endovascular repair (e.g., procedures to treat retrograde dissections, losses of patency, losses of device integrity, endoleaks, migrations, aortic expansions, aortic ruptures) and any deaths related to the treated pathology or endovascular graft (e.g., aneurysm rupture, retrograde dissection leading to fatal cardiac tamponade), unless evidence is available to demonstrate that the death is not lesion related	30 days or in-hospital for index endovascular procedures	
Permanent paraplegia	Paraplegia secondary to spinal cord ischemia identified within 30 days of the index endovascular procedure combined with spinal cord ischemia scale grade of "3" at the one-month follow-up visit. The grading system for spinal cord ischemia is described in TEVAR reporting standards	Event reported within 30 days of endovascular procedure without resolution at one month follow-up	
Permanent paraparesis	Paraparesis secondary to spinal cord ischemia identified within 30 days of the index endovascular procedure combined with spinal cord ischemia scale grade of "2" at the one-month follow-up visit. The grading system for spinal cord ischemia is described in TEVAR reporting standards	Event reported within 30 days of endovascular procedure without resolution at one month follow-up	
New onset renal failure requiring dialysis	New onset sustained renal failure identified within 30 days of the index endovascular procedure, combined with need/requirement for dialysis at the one month follow-up visit	Event reported within 30 days of endovascular procedure without resolution at one month follow-up	
Severe bowel ischemia	Bowel ischemia resulting in bowel resection or fatal outcome	30 days	
Disabling stroke	Stroke was assessed using the Modified Rankin Scale. Stroke identified as having occurred within 30 days of the index endovascular procedure, combined with mRS $\geq 2$ with an increase from baseline of at least one grade at 90 days  Modified Rankin Score was completed by an allied health staff member who successfully completed mRS certification or licensed medical professional	120 days (30 days for Stroke Events, plus 90 days for mRS measurements)	

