3.2 Control Arm(s)

There are no control arms in this study.

4. Study Data Collection

Subjects will be evaluated, at a minimum, using the schedule of events described in Table 4. The timing of study evaluations will be done according to the schedule defined in Table 5. Investigators will be held responsible for the performance of all Protocol-required testing at their respective time points, including testing done at institutions different than the implanting study site. It is highly recommended that subjects return back to their centers of enrollment for follow-up evaluations to foster testing compliance and continuity of care.

Sites are to schedule all study testing to be performed within the ideal visit window; however, any available data collected in the analysis window will be summarized as occurring within the given window. Data collected outside the ideal window, but within the analysis window will not be considered a protocol deviation.

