**Table 5: Follow-up Visit Ideal and Analysis Window Definitions**

Follow-up Visit	Ideal Window (days)	Analysis Window (days)
Procedure	0	0
Discharge*	Before hospital discharge	N / A
Post-Procedure	Not required	1-14
1 Month	23-44	15-59
3 Month	76-104	60-126
6 Months	150-210	127-242
12 Months	275-455	243-546
24 Months	640-820	547-911
36 Months	1005-1185	912-1275
48 Months	1370-1550	1276-1640
60 Months	1735-1915	1641-2006

\*Follow-up visit is categorized as "Discharge" through initial hospitalization, regardless of length.

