## 5. Statistical Analyses

### 5.1 Analysis Populations

The following populations will be used in various analyses of the data collected in the AAA 17-01 study:

1. All Enrolled Subjects - This population will consist of all enrolled Subjects. A patient is considered enrolled into the study once the Main informed consent has been signed and dated.
2. All Enrolled and Implanted Subjects - This population will consist of all enrolled and implanted Subjects. A patient is considered enrolled into the study once the Main informed consent has been signed and dated, and successfully implanted with the study device (TAMBE in the primary arm, CTAG + TAMBE in the secondary arm).
3. Uncomplicated Technical Success Eligible Population (each study arm) [Per protocol population] - This population will consist of enrolled and implanted Subjects with a follow-up visit at or after 30 days following initial TAMBE Device implant procedure. Additionally, any Subjects with an eligible technical success event, as defined in **Section 2.3.1**, even if they did not complete a follow-up visit at or after 30 days following initial procedure, will be included.
4. Clinically Significant Reintervention / Lesion Related Mortality Population (each study arm) - This population will consist of enrolled and implanted Subjects that have completed the 12 month analysis window. Additionally, any Subjects with an eligible clinically significant reintervention event, as defined in **Section 2.3.1**, even if they did not complete the necessary follow-up visit or imaging to otherwise be included in the population, will be included.
5. Secondary Effectiveness Populations (each study arm, each endpoint) - These populations will consist of enrolled Subjects with an evaluable result for the specific variable.
6. Reduced Profile VBX Population – This population will consist of the subjects in the Continued Access Phase who had been implanted with at least one reduced profile VBX device.

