#### 5.4 Statistical Analysis of Endpoints

One-sided exact Clopper-Pearson confidence intervals for binomial proportions ( $\alpha=0.05$ ) will be constructed to test the Uncomplicated Technical Success and Clinically Significant Reintervention hypotheses in the Primary Study Arm. The null hypothesis for each endpoint will be rejected if the lower bounds of the 95% confidence interval exceeds the corresponding performance goal. This is equivalent to stating that the estimated effectiveness and safety must exceed the PG with a Type I error rate ( $\alpha$ ) of  $< 0.05$ .

Primary and Secondary Endpoints will be summarized in the Secondary Study Arm, but no hypotheses tests will be performed.

All events must meet the protocol definition.

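### Permanent paraplegia, paraparesis and dialysis are scored at a one-month visit that can precede day 30 or, after a very long stay, not exist, and the plan's passages support different scores for the same subject

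*Combined protocol and SAP*

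**What the plan says.** SAP Section 2.3.1, Table 1, defines three Procedural Safety components by two joint conditions: the event is identified within 30 days of the index procedure, and it is present at a named visit. For dialysis the second condition is "combined with need/requirement for dialysis at the one month follow-up visit". For paraplegia it is a "spinal cord ischemia scale grade of '3' at the one-month follow-up visit"; paraparesis is worded the same way with grade 2. The timing column of the same rows is worded differently: "Event reported within 30 days of endovascular procedure without resolution at one month follow-up".

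Section 4.2, Table 5, gives the one-month visit an ideal window of days 23-44 and an analysis window of days 15-59. Its footnote says: "Follow-up visit is categorized as 'Discharge' through initial hospitalization, regardless of length". The Discharge row has no analysis window. Section 4, on the other hand, says that "any available data collected in the analysis window will be summarized as occurring within the given window".

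Section 5.1, item 3, builds the denominator from implanted subjects "with a follow-up visit at or after 30 days following initial TAMBE Device implant procedure", plus any subject with an eligible event. Section 5.4 adds: "All events must meet the protocol definition".

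**The concern.** The period for identifying an event runs to day 30, but the visit that confirms persistence may already be over by then. An event that starts after an early visit cannot have been present at it. At the other extreme, a subject whose first hospitalization lasts past day 59 may have no assessment labelled one-month at all, and paraplegia or dialysis is a plausible reason for such a stay. In both cases any later visit, such as month 3, brings the subject into the denominator, and under the Definition column the subject is then a non-event. An early visit can also err the other way, because a deficit only days old is called permanent.

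These components feed the first co-primary endpoint, which is tested against a fixed 80% goal in a single arm. There is no control group in which the same scoring rule would apply equally, so scoring errors pass directly into the comparison with the goal.

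**Working it through.** **1. Timing, from Tables 1 and 5**

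- Visit on day 23 (ideal window): onset on days 24-30 is inside the event period but after the visit, which is 30 − 23 = 7 days.
- Visit on day 15 (analysis window only): onset on days 16-30, which is 30 − 15 = 15 days.
- Onset on day 21, visit on day 23: the deficit is two days old and meets the definition of permanent.
- First hospitalization past day 59: under the footnote every assessment up to discharge is labelled Discharge, and the one-month window has closed by then.

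**2. The same subject under each passage**

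| Subject | Table 1, Definition column | Table 1, timing column | Section 4 data-window rule |
|---|---|---|---|
| Visit day 23, paraplegia from day 26, next record in month 3 | Non-event | Can be read as an event, since resolution was never shown | No help: no further record by day 59 |
| Same, with a further record on days 30-59 | Unclear which record is the visit | Event if unresolved | The further record is one-month data; event if the deficit is present |
| In hospital past day 59, on dialysis throughout | Non-event if the footnote governs | Event | In-hospital data from days 15-59 are one-month data; event. Conflicts with the footnote |

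**3. The plan's own figures**

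- Implanted number: 86 / 0.85 = 101.2, rounded up to 102. This matches Section 2.6.
- Reintervention endpoint, exact one-sided test at n = 86 against 0.68: pass mark 66, power 81.48% if the true rate is 0.80. This matches. The 0.80 is back-solved, because the assumptions section (2.5) is not readable in the file.
- Safety endpoint at n = 86: the stated power of 93.41% needs a true rate of about 0.923. That is compatible with the plan but not independently confirmed.

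**4. How close one subject is to the result**

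The pass mark is the smallest r with P(X ≥ r | n, 0.80) ≤ 0.05, which is the same as the one-sided 95% Clopper-Pearson lower bound exceeding 0.80.

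- n = 86: 76 successes give a lower bound of 0.8107 (pass); 75 give 0.7972 (fail).
- n = 102: 89 give 0.8050 (pass); 88 give 0.7938 (fail).

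**5. Sensitivity, on an assumed mis-scoring rate**

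Suppose true success is exactly 80% and a net share m of subjects are failures scored as successes. The chance of passing is P(X ≥ r | n, 0.80 + m).

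| m (assumed) | n = 86 | n = 102 |
|---|---|---|
| 0 | 3.0% | 3.9% |
| 1% | 4.8% | 6.4% |
| 2% | 7.6% | 10.2% |

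Here 1% and 2% correspond to 0.86 and 1.72 subjects at n = 86, and to 1.02 and 2.04 at n = 102. No figure in the documents supports any particular m.

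**The case against.** A reader might infer that real events will be scored as successes and that the rule therefore biases the trial towards the device. The documents do not support that much.

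- The timing column asks only that the event has not resolved, and Section 5.4 does not say which column is the definition. On that reading many of these events count.
- Section 4 assigns any data from days 15-59 to the one-month window. A subject seen early can still supply one-month data later in that window, and in-hospital data can qualify. The long-stay problem therefore needs a stay past day 59, or the footnote overriding Section 4. A subject discharged sooner can still have a one-month visit.
- A subject with no visit from day 30 onwards and no eligible event is excluded, not counted as a success. Death during the index hospitalization counts as lesion-related unless shown otherwise.
- Table 4, footnote a, allows the spinal cord ischemia scale by telephone.
- Early visits also count short deficits as permanent, which works against the device. Nothing shows which error is commoner.
- Any binary endpoint can be flipped by one subject at its boundary. At m = 1% and n = 86 the chance of passing is still below 5%.
- Handling of an absent visit may lie in the redacted Sections 5.6.2.5 and 5.6.2.7, or in clinical protocol Sections 3.3 and 9.4, which are cited but not supplied.

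All of this limits the claim, but it does not remove the defect. The data-window rule does not help a subject with late onset and no further record by day 59. The telephone provision is for subjects unable to return, not for those seen too early, and it does not mention dialysis. The plan already deals with the same issue for disabling stroke: Table 4, footnote b, sets the persistence assessment by the date of the suspected event, not by a routine visit. The other three persistence-based components have no counterpart.

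**Conclusion.** The point holds as a defect in the scoring rule. Under the Definition column, a compliant visit schedule can turn an event inside the 30-day period into a non-event, and can label a deficit of a few days permanent. Other passages support a different score for the same subject, so the outcome depends on which passage the adjudicators follow.

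The number affected cannot be derived and is probably small, and a net bias in either direction is not shown. The 1-2% range is an assumption used only for scale. What can be shown is that at the boundary (76/86 against 75/86, or 89/102 against 88/102) one mis-scored subject decides a co-primary test. The conclusion rests on the visible text and could change if the redacted or unsupplied sections settle how an early, missed or in-hospital one-month assessment is scored. The change should be made, because the ambiguity sits in a co-primary safety endpoint and costs little to remove.

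**What to change.** Amend Table 1, in both the Definition and timing columns, for these three components:

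1. Score persistence from an assessment on or after day 30 and within the one-month analysis window (to day 59), in any setting including inpatient, with telephone allowed for the spinal cord ischemia scale. Say which assessment governs if there are several.
2. State that the Discharge label in Table 5 does not govern this scoring, which also settles the conflict with Section 4.
3. Count an event identified within 30 days with no documented resolution by day 59 as an endpoint event.

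The upper limit matters. An open-ended rule using the first assessment from day 30 onwards could draw on the month 3 window, which runs to day 126, and so drop dialysis that was still needed at day 30 but had stopped by then.

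The cost is wording in Tables 1 and 5, a note to the event committee, and an occasional extra contact when the one-month visit was early. The reported success rate may be slightly lower.

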**Table 2: Summary of Clinically Significant Reintervention / Lesion Related Mortality Co-Primary Endpoint**

Outcome	Definition (per Clinical Protocol Section 3.3)	Endpoint Time Evaluated	Final Source Data
Clinically Significant Reintervention			
Clinically-Indicated Condition	An untreated device seal zone endoleak, target-lesion growth (> 5 mm in maximum diameter) or post-treatment TAAA rupture without reintervention at the 12 Month window follow-up visit	12 mo f/u visit	Core Lab (aneurysm size and endoleak) CEC Adjudication (TAAA rupture) Site Data (reintervention)
Device Effectiveness	A compromise of a device seal zone or loss of device integrity (e.g., device kink or collapse) requiring placement of an additional stent or stent-graft	12 mo f/u visit	CEC adjudication
Subject Safety	Total occlusion of a device component, use of a bypass graft or the performance of an open conversion in order to maintain bodily vessel function	12 mo f/u visit	
Complicated Device System Prophylaxis	Any device-related intervention requiring hospitalization, or extension of hospitalization, of three days or more	12 mo f/u visit	
Lesion-related mortality			
Lesion-related mortality	All deaths during hospitalization for index endovascular procedure and within 30 days of the index endovascular procedure or any secondary procedures due to the treated pathology, or the effectiveness of the endovascular repair (e.g., procedures to treat retrograde dissections, losses of patency, losses of device integrity, endoleaks, migrations, aortic expansions, aortic ruptures) and any deaths related to the treated pathology or endovascular graft (e.g., aneurysm rupture, retrograde dissection leading to fatal cardiac tamponade), unless evidence is available to demonstrate that the death is not lesion related	12 mo f/u visit	CEC adjudication

2.3.2 Secondary Endpoint(s)

Table 3 contains the definitions, endpoint time evaluated and source data for the secondary endpoints. The majority of definitions in Table 3 are sourced from the Clinical Protocol Section 3.3. Secondary Endpoint items marked with an asterisk (\*) are defined by this document.

**Table 3: Secondary Endpoint Definitions**

Outcome	Definition	Endpoint Time Evaluated	Final Source Data
Standard Procedure / Hospitalization Metrics			
Aneurysm-related mortality	Defined as all deaths during hospitalization for index endovascular procedure and within 30 days of the index endovascular procedure or any secondary procedures due to the treated pathology, or the effectiveness of the endovascular repair (e.g., procedures to treat retrograde dissections, losses of patency, losses of device integrity, endoleaks, migrations,	30 Days	CEC

Outcome	Definition	Endpoint Time Evaluated	Final Source Data
	aortic expansions, aortic ruptures) and any deaths related to the treated pathology or endovascular graft (e.g., aneurysm rupture, retrograde dissection leading to fatal cardiac tamponade), unless evidence is available to demonstrate that the death is not lesion related.		
Individual elements of Procedural Safety 
 
• Aortic Rupture
 
• Lesion-related mortality
 
• Permanent paraplegia
 
• Permanent paraparesis
 
• New onset renal failure requiring dialysis
 
• Severe bowel ischemia
 
• Disabling stroke
 
	Reference Table 1 for definitions for these elements	Reference Table 1	Reference Table 1
Procedural blood loss	Estimated Blood Loss during Index Procedure (mm)*	Index Procedure	Site
Access-related complications	An Adverse Event determined by Site to be related to vascular access*	30 Days	Site
Procedural time	Duration of Index Procedure (minutes) [the time of incision will indicate the start time and the finish time is the time of closure ]. *	Index Procedure	Site
Stage Procedure Time	Duration of Stage Procedure (minutes) [the time of incision will indicate the start time and the finish time is the time of closure ]. *	Stage Procedure	Site
Length of hospital stay	Number of Days Subject stayed in hospital (from admission date to discharge date). *	Initial Hospitalization of Index Procedure	Site
Stage procedure length of hospital stay	Number of Days Subject stayed in hospital for stage procedure (from admission date to discharge date). *	Stage Procedure	Site
Extended Technical Clinical Success	Subjects who present within the 30-Day follow-up with no Type I or Type III endoleak, as evaluated by CTA, and free from device-related intervention	30 Days	Core Lab
Aortic Stent-Graft Effectiveness Measures			
Type I endoleak	Endoleak arising from the proximal or distal sealing zone of a device perfusing the aneurysm	Through 12 Months	Core Lab
Type IA endoleak	Inadequate seal at the proximal end of the device placed in the aorta	Through 12 Months	Core Lab
Type IB endoleak	Inadequate seal at the distal end of the device placed in iliac vessel	Through 12 Months	Core Lab
Type IC endoleak	Inadequate seal at the distal end of a device placed inside branch vessel	Through 12 Months	Core Lab

Outcome	Definition	Endpoint Time Evaluated	Final Source Data
Type II endoleak	Endoleak arising from a patent branch vessel perfusing the aneurysm, e.g., lumbar or inferior mesenteric branch	Through 12 Months	Core Lab
Type III endoleak	Endoleak arising from the component junction(s) of the prosthesis or due to damage to the graft material perfusing the aneurysm.	Through 12 Months	Core Lab
Type IIIA endoleak	Modular disconnection or apposition failure	Through 12 Months	Core Lab
Type IIIB endoleak	Graft tear	Through 12 Months	Core Lab
Type III General endoleak	A Type III endoleak whose source cannot be differentiated between an intercomponent junction or graft tear	Through 12 Months	Core Lab
Type IV endoleak	Endoleak of whole blood through the graft fabric perfusing the aneurysm	Through 12 Months	Core Lab
Indeterminate endoleak	Endoleak perfusing the aneurysm without a definitive source	Through 12 Months	Core Lab
Device Migration	Longitudinal movement of all or part of the device for a distance $\geq 10$ mm, as confirmed by CT scan, relative to anatomical landmarks and device positioning at the first post-operative CT scan	Through 12 Months	Core Lab
TAAA enlargement	An increase in the maximum aneurysm diameter of 5 mm or more relative to the first post-operative CT scan within the 30 day follow-up window	Through 12 Months	Core Lab
Severe distal thromboembolic events	Ischemic events related to the device from tissues distal to the device implantation site sufficiently debilitating to necessitate bypass, open surgical intervention, limb amputation or leading to death	Through 12 Months	CEC
Aortic Rupture	Rupture in the stented segment of the aorta verified with direct observation or CT Scan*	Through 12 Months	CEC
Device or procedure-related laparotomy	An adverse event assessed by the site as being device or procedure-related that led to a laparotomy *	Through 12 Months	Site
Conversion to open repair	A reintervention that resulted in explant of the device and open surgical repair*	Through 12 Months	Site
Aortoiliac device limb occlusion	An occlusion in the distal bifurcated component, contra-lateral limb component, contra-iliac extender component, or the ipsi-lateral extender component*	Through 12 Months	Core Lab
Loss of device integrity	Defined as any of the following: 
 
Wire fracture identified in the sealing row stents of either the aortic, branch or iliac components
 
Transient (compression) or permanent stent-graft collapse (invagination) following complete
 
	Through 12 Months	Core Lab

Outcome	Definition	Endpoint Time Evaluated	Final Source Data
	device deployment, resulting in an overall reduction in the aortic, branch or iliac vessel luminal diameter		
Primary patency Adapted Study Definition	Blood flow without occlusion maintained through the device after implant without an intervention.	Through 12 Months	Site and Core Lab
Assisted primary patency Adapted Study Definition	Blood flow maintained through the device after implant regardless of re-interventions performed (without occlusion)	Through 12 Months	Site and Core Lab
Secondary patency Adapted Study Definition	Blood flow through the device regardless of reinterventions performed (with or without occlusion) and freedom from surgical bypass	Through 12 Months	Site and Core Lab
All reinterventions	An additional unanticipated interventional or surgical procedure (including conversion to open surgery), related to the device (including withdrawal of the delivery system) or procedure. Anticipated or unanticipated status will be determined at the discretion of the investigator.  These will not include unanticipated, corrective intervention at the access site(s), or device intervention to address non-treatment area issues	Through 12 Months	Site
Branch Vessel Device Effectiveness Measures			
Branch vessel patency	Primary, Assisted Primary, Secondary Patency	12 Months	Site and Core Lab
Acute kidney injury	>50% decrease in eGFR within 30 days of TAMBE Device treatment when compared to pre-treatment serum creatinine value	30 days	Site
Renal function deterioration	A sustained >25% decrease in eGFR over two consecutive study visits following TAMBE Device treatment when compared to pre-treatment serum creatinine value	12 Months	Site

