**Table 1: Summary of Uncomplicated Technical Success Primary Endpoint**

Outcome	Definition (per Clinical Protocol Section 3.3)	Endpoint Time Evaluated	Final Source Data
Uncomplicated Technical Success			
Successful access and delivery	
All Gore devices are successfully tracked from the access site to the intended implantation site and released from the deliver catheter successfully without the need for unanticipated corrective intervention related to delivery.
	TAMBE Device Index procedure	Site data
Successful and accurate deployment	
Deployment of all required endovascular device components in the planned location:
 
 
- Patency of required aortic endovascular grafts with absence of device deformations (e.g., kinks) requiring unplanned placement of a non-TAMBE device component* within the endovascular graft;
 
- Patency of all branch devices with absence of device deformations (e.g., kinks) requiring unplanned placement of any non-TAMBE device component* within the branches**;
 
 
* TAMBE components include the aortic component, distal bifurcated component, iliac extenders, contralateral legs, VBX component and CTAG Device.
 
**Implantation of bare metal stents to smooth the transition from the VBX to the uncovered branch vessel will not count against technical success if the procedure otherwise meets the definition of technical success. Use of non-TAMBE devices to correct iatrogenic complications in the treated aorta or branch vessels would be considered technical failures.
	TAMBE Device Index procedure	Site Reported and CEC Adjudication 
Successful withdrawal	Successful withdrawal of the delivery systems, without a need for corrective intervention related to withdrawal	TAMBE Device Index procedure	Site data
Procedural Safety			

Outcome	Definition (per Clinical Protocol Section 3.3)	Endpoint Time Evaluated	Final Source Data
Aortic Rupture	Rupture in the stented segment of the aorta verified with direct observation or CT scan	30 days	CEC adjudication

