4.1 Study Collection Intervals

Subjects will be asked to return for follow-up visits at one (1), three (3), six (6), 12, 24, 36, 48, and 60 months post-treatment. At each follow-up visit, subjects will undergo an evaluation for adverse events.

Table 4: Schedule of Events

	Pre-treatment (Screening)	Treatment	Hospital Discharge	One Month	Three Months	Six Months	Annually through 5 Years
Informed Consent	X						
Demographics and Medical History	X						
Risk Scales (ASA, NYHA, SVS)	X						
Physical examination	X		X	X	X	X	X
Adverse Events	X	X	X	X	X	X	X
Medication Review	X		X	X	X	X	X
Modified Rankin Scale a,b	X		X	X	X if applicable	X	
Spinal Cord Ischemia Scale a	X		X	X		X	

NIH Stroke Scale c	X		X If applicable				
SF-36 Questionnaire	X			X	X	X	X
Serum Creatinine Concentration	X		X	X	X	X	X
Spiral CTA (contrast) d	X			X		X	X
Spiral CT (non-contrast)				X		X Optional	X Optional
Completion Angiogram		X					
Magnified Branch Visualization		X					
Abdominal Ultrasound	X		X	X	X	X	X
Multiplanar Device Radiographs (X Ray)				X		X	X

a If subject is unable to return to the site for a follow-up visit, they may be contacted by telephone to evaluate the Modified Rankin Scale and Spinal Cord Ischemia Scale.

b For subjects suspected of having a stroke event within 30 days following the index endovascular procedure an additional mRS score should be completed at 90 days following the suspected stroke event but no greater than 120 days post index endovascular procedure.

c NIH Stroke Scale should be performed for any subject suspected of having a stroke event that undergoes the treating site's stroke protocol during the study interval from the initiation of the index endovascular procedure until discharge. The scale should be performed as soon as possible after learning of the suspected event and again at the time of discharge.

d CTA of chest/abdomen/pelvis at Screening. CTA of abdomen and pelvis at all follow-up visits, except for Secondary Study Arm Subjects who must have a CTA of chest/abdomen/pelvis at all visits. MRA may be used in place of CTA during follow-up if the Subject is contraindicated for CTA.

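### Extended Technical Clinical Success is scored only in subjects with an evaluable 30-day CTA, so early deaths and other early failures can leave the denominator instead of counting as failures

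*Combined protocol and SAP*

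**What the plan says.** Table 3 (SAP section 2.3.2) describes the endpoint as "Subjects who present within the 30-Day follow-up with no Type I or Type III endoleak, as evaluated by CTA, and free from device-related intervention". It is evaluated at 30 days, and the only final source listed is the Core Lab. The row mentions neither survival nor a denominator.

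The denominator comes from section 5.1, item 5, on the secondary effectiveness populations: "These populations will consist of enrolled Subjects with an evaluable result for the specific variable". Nothing more is said about subjects without a result.

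The two co-primary populations in the same section are built differently. Item 3 requires a visit at or after 30 days, but subjects with an eligible event, "even if they did not complete a follow-up visit at or after 30 days following initial procedure, will be included". Item 4 has a parallel clause for the 12-month endpoint that also covers missing imaging.

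On data sources, Table 2 splits the clinically indicated condition by who holds the data: "Core Lab (aneurysm size and endoleak) CEC Adjudication (TAAA rupture) Site Data (reintervention"). In Table 3 the row for all reinterventions is sourced from the site, and the patency rows, which depend on interventions, from site and Core Lab.

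**The concern.** A 30-day success rate should fall when subjects die or fail before day 30. Here the success criterion needs a CTA, and the population needs an evaluable result. A subject who dies before the scan has no CTA, so that subject is removed and not scored as a failure. The same can happen to a subject who is converted to open repair, or who has a device-related intervention and is not scanned afterwards. These are the worst early outcomes, so the omission favours the device.

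At stake is how the rate reads in a report. A reader will take it as the share of treated subjects who were well at 30 days. As written, it is closer to the share of scanned subjects who were free of leak and intervention.

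A smaller matter is that freedom from intervention is half of the definition, yet the source cell names only the Core Lab, while other rows take reinterventions from the site.

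**Working it through.** The plan states no expected rate, sample size or power for this endpoint, so there is no figure to reproduce. The check has two parts.

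**1. Populations side by side (section 5.1)**

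| Population | Base requirement | Keeps subjects with an event but no visit or imaging? |
|---|---|---|
| Item 3 (co-primary 1) | Visit at or after 30 days | Yes |
| Item 4 (co-primary 2) | 12-month window completed | Yes |
| Item 5 (secondary endpoints) | Evaluable result for the variable | No such clause |

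**2. Size under assumed values**

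Inputs:
- N = 102, the Primary Study Arm size (sections 2 and 5.3).
- d = deaths before the CTA; assumed 2, 4 or 6.
- k = scanned subjects with a Type I/III endoleak or a device-related intervention; assumed 10, with 5 as a second case.

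Formulas:
- As written: (N − d − k) / (N − d)
- Deaths as failures: (N − d − k) / N
- Gap: the difference, which equals the as-written rate × d/N

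| k | d | As written | Deaths as failures | Gap (points) |
|---|---|---|---|---|
| 10 | 2 | 90/100 = 90.0% | 90/102 = 88.2% | 1.8 |
| 10 | 4 | 88/98 = 89.8% | 88/102 = 86.3% | 3.5 |
| 10 | 6 | 86/96 = 89.6% | 86/102 = 84.3% | 5.3 |
| 5 | 2 | 95/100 = 95.0% | 95/102 = 93.1% | 1.9 |
| 5 | 4 | 93/98 = 94.9% | 93/102 = 91.2% | 3.7 |
| 5 | 6 | 91/96 = 94.8% | 91/102 = 89.2% | 5.6 |

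With k = 10, tripling the deaths from 2 to 6 moves the as-written rate by 0.4 points and the corrected rate by 3.9. The gap is close to d/N and depends little on k. A subject converted or reintervened on and never scanned acts in the same way as a death, so d can be read as all such events.

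Missing scans are a separate matter. Suppose 5 more subjects are alive and event-free but have no scan, with d = 2 and k = 10. There are then 85 successes and three possible rates:
- evaluable subjects only: 85/95 = 89.5%;
- deaths added as failures: 85/97 = 87.6%;
- every subject without a scan a failure: 85/102 = 83.3%.

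The endpoint row on its own does not choose between these. Item 5 points to the first.

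**The case against.** **The row can be read the other way.** Someone who dies does not present, so the row could be a numerator over all subjects, with non-presenters as failures. The term evaluable is not defined. Table 3 also says "The majority of definitions in Table 3 are sourced from the Clinical Protocol Section 3.3", and this row is not marked as defined by the SAP itself; that protocol section is not in the reviewed documents. The sections on attrition and missing data are redacted. Any of these may hold a rule. This stands as a limit on certainty, but the visible text still leads to the evaluable-only denominator.

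**Not every early death drops out.** The 1-month analysis window opens on day 15 (Table 5), so a subject can be scanned, die before day 30 and stay in as a success. This also stands. It changes which deaths are missed, but those deaths still do not count as failures.

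**The impact is limited.** Section 2.3.1 states hypothesis tests for the co-primaries only. In-hospital and 30-day deaths are covered by lesion-related mortality in both co-primaries and by a separate 30-day mortality row, which counts "all deaths during hospitalization for index endovascular procedure and within 30 days of the index endovascular procedure" unless shown not to be lesion-related. This stands in full.

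**Stronger readings that the documents do not support:**
- *The rate rises as early deaths increase.* With k fixed it falls slightly: with k = 4, it goes from 98/102 = 96.1% at no deaths to 95/99 = 96.0% at three. It would rise only if those who die would more often have had leaks, and nothing in the documents shows that.
- *Index technical failures are wrongly counted as successes.* Table 1 says "Use of non-TAMBE devices to correct iatrogenic complications in the treated aorta or branch vessels would be considered technical failures", and such a subject could be leak-free at 30 days. But no passage makes this endpoint conditional on index technical success. Device-related intervention also has no stated start, so some corrective placements at the index procedure may already count as failures.
- *Subjects imaged by MRA have no result.* The footnote to Table 4 says "MRA may be used in place of CTA during follow-up if the Subject is contraindicated for CTA", which plausibly already covers them.
- *The planning rate for co-primary 1 bounds the error.* The rate that reproduces the stated 93.41% power is about 92.3%, but it is back-solved and belongs to a composite that includes paraplegia, dialysis and stroke. Its complement says nothing about this endpoint.
- *The Core Lab cannot hold intervention data.* Its role is set out in a protocol section that is not in the reviewed documents. What can be shown is only that the source cell differs from comparable rows.

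**Conclusion.** The point holds as a defect in the denominator. Followed as written, section 5.1 item 5 lets subjects with an early failure and no 30-day scan leave the analysis, although the plan guards both co-primaries against this. The resulting rate hardly responds to early deaths.

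The size is illustrative. With 102 subjects and 2 to 6 deaths before CTA, the overstatement is about 1.8 to 5.3 points at 10 leaks or interventions, and about 1.9 to 5.6 points at 5. The death and leak counts are assumptions, and the conclusion rests on there being no contrary rule in the protocol definitions or the redacted sections.

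The incomplete source cell is a real but minor inconsistency. Study success rests on the co-primaries (section 1.1) and does not change.

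**What to change.** 1. **Population.** For this endpoint, add to section 5.1 item 5 the clause used in items 3 and 4. The denominator becomes all implanted subjects with either a readable 30-day study or a failure event.
2. **Scoring.** State in the Table 3 row that death, open conversion or device-related intervention before the assessment counts as failure.
3. **Missing scans.** Report separately the number of subjects with neither a readable study nor a failure event.
4. **Sources.** Change the source cell to Core Lab (endoleak), Site (device-related intervention) and CEC (death).
5. **Optional clarification.** Say whether interventions during the index procedure count, and that MRA under the Table 4 footnote is accepted. Whether to require index technical success is a choice for the sponsor; leaving it out is not an error.

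The cost is one table row and one population clause. Deaths, reinterventions and imaging are already collected for other endpoints. The reported rate will be slightly lower if early failures occur.
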